4.2.14.1 Definition

For all participants, the hypothalamic-pituitary-adrenal (HPA) axis integrity is evaluated after 4 weeks on 5 mg/day and prior to tapering down the OCS dose. If the result of HPA

test is in indeterminate range, the additional ACTH/HPA test is required. More details is given in CSP Section 8.2.1.

The proportion of participants with normal, indeterminate and complete AI based on HPA test, the proportion of participants with normal, partial and complete AI based on ACTH test as well as the proportion of participants with normal, partial and complete AI based on the repeated HPA test are summarised at Week 28 or Week 52.

4.2.14.2 Derivations

The three proportions of participants with normal, indeterminate and complete AI based on morning cortisol test are calculated as the total number of participants with the normal, indeterminate and complete AI respectively divided by total number of participants on the FAS.

The three proportions of participants with normal, partial and complete AI based on ACTH test are calculated as the total number of participants with the normal, partial and complete AI respectively divided by total number of participants requiring additional ACTH testing.

The three proportions of participants with normal, partial and complete AI based on repeated morning cortisol test are calculated as the total number of participants with the normal, partial and complete AI respectively divided by total number of participants requiring repeated morning cortisol testing for whom ACTH test is not available.

Strategies of handling intercurrent events are presented in Section 4.2.

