	• Categorised percent reduction from baseline in the daily maintenance OCS dose (categories: ≥ 90% to ≤ 100% reduction, ≥ 75% to < 90% reduction, ≥ 50% to < 75% reduction, > 0% to < 50% reduction, no change or any increase) at Week 28 and Week 52
	Absolute and percent change from baseline in daily maintenance OCS dose at Week 28 and Week 52
To assess the ability of tezepelumab to improve lung function	Change from baseline in post-BD FEV ₁ at Week 28 and Week 52
To assess the ability of tezepelumab to improve asthma control ^a	Change from baseline in Asthma Control Questionnaire 6 (ACQ-6) at Week 28 and Week 52
To assess the ability of tezepelumab to improve asthma related quality of life	Change from baseline in standardised Asthma Quality of Life Questionnaire for 12 years and older (AQLQ[s]+12) total score at Week 28 and Week 52
	Change from baseline in St. George's Respiratory Questionnaire (SGRQ) total score at Week 28 and Week 52
Safety objective	
To describe the safety and tolerability of tezepelumab	Serious adverse events (SAEs), discontinuation of investigational product due to an adverse event (DAEs), and adverse events of special interest (AESI)

Exploratory objectives	
To describe changes from baseline in biomarker levels	Change from baseline in biomarker levels at Week 28 and Week 52
To assess the ability of tezepelumab 210 mg SC to allow reduction of the prescribed OCS dose without loss of asthma control ^a	Time to 50% reduction of OCS dose at Week 28 and Week 52 Time to 100% reduction of OCS dose at
	Time to 100% reduction of OCS dose at Week 28 and Week 52
To describe the occurrence of AI	Proportion of participants with normal, partial, complete AI at Week 28 and Week 52
To assess the ability of tezepelumab to improve asthma control ^a	Proportion of ACQ-6 responders at Week 28 and Week 52
To assess the ability of tezepelumab to improve asthma related quality of life	Proportion of AQLQ(s)+12 responders at Week 28 and Week 52
	Proportion of SGRQ responders at Week 28 and Week 52
To describe the ability of tezepelumab to	Change from baseline in AIRQ at Week 52
improve Asthma Impairment and Risk Questionnaire (AIRQ TM)	Proportions of AIRQ responders at Week 52
To describe the ability of tezepelumab to improve Sino-nasal Outcome Test (SNOT-22)	Change from baseline in Sino-nasal Outcome Test (SNOT-22) at Week 28 and Week 52
	Proportion of SNOT-22 responders at Week 28 and Week 52

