8.2.1.1 Morning Cortisol Test

The morning cortisol test will be done in all participants 4 weeks after reaching the 5 mg dose of OCS, and before further dose reductions. It is also done 3 months after a participant has completed a test indicating complete AI.

Serum samples for cortisol will be collected between 8 and 9 am and will be sent to a central laboratory for evaluation.

The following values will be used to define AI status for the morning cortisol test:

Table 9 Cortisol Status

AI status	SI units	Participants taking oestrogen- containing contraceptives
Normal	>350 nmol/L	>700 nmol/L
Indeterminate results	100 - 350 nmol/L	200 - 700 nmol/L
Complete AI	<100 nmol/L	<200 nmol/L

Once the results are available, the site will inform the participant of the results via telephone. For sites where tetracosactides are available, and depending on the result, the actions that will be implemented are as follows:

- If cortisol levels are within normal range and the participant does not exhibit any signs and/or symptoms of AI, the participant will continue OCS down-titration by 2.5 mg Q4W
- If cortisol levels are within normal range but the participant exhibits signs and/or symptoms of AI, then OCS down-titration should continue at a slower pace (1 mg Q4W).
- If cortisol levels are below the normal range and above the complete AI range (indeterminate result), then the participant will be instructed to maintain the current OCS dose and come back to the site within 1 week for an ACTH stimulation test (Section 8.2.1.2)
- If complete AI is confirmed, sites will inform participant that the OCS dose will remain the same without further reduction until there is evidence of recovery from the complete AI without worsening of asthma control. The morning cortisol test and associated clinical assessments (see Table 1) will be repeated 3 months later. After the repeat morning cortisol test, the site will inform the participant based on the results as follows:
 - If morning cortisol results indicate normal cortisol values, then reductions will be 2.5 mg Q4W, and the participant would subsequently move to maintenance at the OCS lowest possible dose
 - If morning cortisol results are indeterminate, then reductions will be delayed further, and the participant would return approximately 1 week later for an ACTH stimulation test:
 - o If normal result after ACTH stimulation (Table 10): reduce by 2.5 mg Q4W then move to maintenance at the lowest possible dose

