3.3 General Considerations

In general, continuous endpoints are summarised using the mean, the standard deviation, median, minimum value, and maximum value, and the categorical endpoints are summarised using frequency counts and percentages, as well as a two-sided 95% CI for proportions computed using exact Clopper-Pearson method. Time to event data is presented graphically using Kaplan Meyer curve.

Absolute change from baseline is defined as (post-baseline value – baseline value). The percent change from baseline is defined as {(post-baseline value – baseline value)/baseline value)}*100. Baseline calculations are defined in the Section 3.3.1.2.

For participants' proportion calculation, the denominator is the number of participants in the Full Analysis Set defined in Section 4.1.2 unless otherwise stated.

No imputation performed beyond the approach defined for outcome measures. Imputation for partial date is detailed in the Appendix A.

Unless specified otherwise, the daily maintenance OCS dose, including the daily OCS at baseline (Section 3.3.1.2) and the final daily OCS dose (Section 4.2.1.2), is defined based on the prescribed maintenance dose of OCS, expressed as a dose per day, at the time of the relevant visit. If a participant is on a fixed daily dose, then the OCS dose is defined as that prescribed dose. If the participant is on every other day regimen (or different doses every other day), then the OCS dose is defined as the average amount prescribed to be taken each day. For example, should a participant be on a 10 mg every other day regimen of OCS, their OCS dose is defined as 5 mg.

Maintenance dose of OCS is collected on the ECSYSCRT eCRF page with a therapy reason of "Asthma maintenance dose", "Titration, due to asthma", "AI based on cortisol test", "Signs/symptoms of AI" and "Adrenal crisis". If the maintenance OCS doses with more than one therapy reasons (including only those mentioned earlier) are prescribed on the same day (e.g., "Asthma maintenance dose" and in addition "Signs/symptoms of AI"), then the sum of the doses are calculated.

Note that the prescribed OCS dose with therapy reason of "Asthma exacerbation per protocol" or "Worsening of asthma, without exacerbation" is not included in the daily OCS dose calculation. In case of overlapping OCS doses taken for asthma worsening or exacerbation with maintenance doses of OCS, the latter one is excluded from the daily OCS dose calculation.

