4.2.1.7 Subgroup Analyses

The number and proportion with 95CI%, as described in Section 4.2.1.4, is also presented by the following pre-specified subgroups for both primary (Week 28) and final (Week 52) analysis:

- Eosinophils (EOS) at baseline group: $< 300/\mu L, \ge 300/\mu L$
- Eosinophils (EOS) at baseline group: $< 150/\mu L, \ge 150/\mu L$
- Eosinophils (EOS) at baseline group: <150, >=150 to <300, >=300
- Eosinophils (EOS) at screening group: <150 with documented high EOS, $<150/\mu$ L without documented high EOS, $>=150/\mu$ L
- Baseline FeNO group: $< 25 \text{ ppb}, \ge 25 \text{ ppb}$
- Baseline (Any) specific IgE status (FEIA): Any FEIA positive, All FEIA negative, Unknown FEIA (see Section 4.1.5.1)
- Baseline perennial specific IgE status (FEIA): Any perennial FEIA positive, All perennial FEIA negative, Unknown perennial FEIA (see Section 4.1.5.1)
- Baseline seasonal specific IgE status (FEIA): Any seasonal FEIA positive, All seasonal FEIA negative, Unknown seasonal FEIA (see Section 4.1.5.1)
- Eosinophils (EOS) at baseline and baseline perennial specific IgE status (FEIA):
 - \circ EOS < 150/ μ L and with any perennial FEIA positive
 - EOS $\geq 150/\mu$ L to $< 300/\mu$ L and with any perennial FEIA positive
 - EOS $\ge 300/\mu$ L and with any perennial FEIA positive
 - O EOS < 150/μL and with all perennial FEIA negative
 - o EOS ≥ $150/\mu$ L to < $300/\mu$ L and with all perennial FEIA negative
 - EOS $\ge 300/\mu$ L and with all perennial FEIA negative
- Daily OCS dose at baseline: (≤10 mg versus >10 mg prednisone or prednisolone)
- Regions: Central/Eastern Europe (low availability of biologics), Western Europe (high availability of biologics), South America, North America (see Section 4.1.1.1)

- Therapy reason for SCS use related to AI: Yes (includes the following therapy reasons: AI based on cortisol test, Signs/symptoms of AI, Adrenal Crisis), No (all remaining therapy reasons)
- Access to ACTH Test (ACTH is not available in Poland, Bulgaria and Latvia, ACTH available in all the remaining countries)

For the final (Week 52) analysis additionally the following subgroups will be presented:

- Adrenal Insufficiency status measured when a participant reaches 5mg of daily OCS dose: Normal, Partial AI, Complete AI.
- Countries: for the list of countries see Section 4.1.1.1

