4.2.14.3 Handling of Dropouts and Missing Data

No data imputation.

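### Morning-cortisol adrenal insufficiency percentages are divided by the whole FAS although only participants who taper to 5 mg/day are tested, so each is diluted by the untested share

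*SAP*

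**What the plan says.** The endpoint in Protocol section 3 is "Proportion of participants with normal, partial, complete AI at Week 28 and Week 52", listed among the exploratory objectives. SAP section 4.2.14.2 splits it into three sets of proportions with different bases:

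- Morning cortisol: participants with normal, "indeterminate and complete AI respectively divided by total number of participants on the FAS".
- ACTH stimulation test: counts "divided by total number of participants requiring additional ACTH testing".
- Repeated morning cortisol: counts divided by the "total number of participants requiring repeated morning cortisol testing for whom ACTH test is not available".

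Testing is conditional. Protocol section 8.2.1.1 states: "The morning cortisol test will be done in all participants 4 weeks after reaching the 5 mg dose of OCS". For a baseline dose of 5 mg the test falls four weeks after the first tezepelumab dose (Protocol section 8.2.1). SAP section 4.2.1.7 describes the same timing: "Adrenal Insufficiency status measured when a participant reaches 5mg of daily OCS dose".

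The FAS is the general default. SAP section 3.3 says "the denominator is the number of participants in the Full Analysis Set defined in Section 4.1.2 unless otherwise stated". For missing data, SAP section 4.2.14.3 says only "No data imputation". Section 4.2.14.4 asks for numbers and proportions over time on the FAS and specifies no row for untested participants. The FAS-based responder tables in SAP sections 4.2.15.4 to 4.2.19.4 do show missing data as a category.

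**The concern.** Entry doses run from 5 to 40 mg/day (Protocol section 5.1). A participant held above 5 mg by loss of asthma control, or who withdraws during the taper, is never tested. That participant has no AI status, yet counts in the denominator of every morning-cortisol row. The opening statement of SAP section 4.2.14.1 that all participants are evaluated does not change this, because it is qualified by the four weeks on 5 mg/day.

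At stake is the answer to a stated objective, describing the occurrence of AI. Protocol section 2.1 treats an impaired cortisol response as potentially life-threatening. Protocol section 8.3.5 does not record signs and symptoms of AI unless they are an SAE, DAE or AESI, so these test results are the main systematic evidence on AI. A denominator that makes complete AI look rarer errs in the less cautious direction.

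**Working it through.** **The plan's own figure.** The documents state no figure for this endpoint. Their only planning figure is the Clopper-Pearson half-width of 5.8 points at 50% with n = 300 (Protocol section 9.2). Exact limits for 150/300 give 5.80 points, so it reproduces. The same interval method is used below.

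**Formula.** Let N be the FAS size, r the share of the FAS with a morning cortisol result, and p the proportion of the tested in a given category.

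- SAP percentage = (N × r × p) / N = r × p
- Percentage among the tested = p
- Relative understatement = (p − r × p) / p = 1 − r
- Sum of the three rows = r, because the three values of p sum to 1

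The factor r is the same for the normal, indeterminate and complete-AI rows, so ratios between rows are unchanged.

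**Inputs.** N = 300 (Protocol section 9.2). The documents give neither r nor p for this trial, so both are assumptions:

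- r = 50% is borrowed from the planning success rate (Protocol section 9.2).
- r = 81% is borrowed from the earlier open-label benralizumab trial described in Protocol section 2.1.
- r = 90% and 100% are further illustrations.
- p = 10% is an illustrative complete-AI rate; 25% is shown once for sensitivity.

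The last column asks what the complete-AI share of the FAS would be if every untested participant had it.

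| r | Tested | p | Complete AI | SAP: out of 300 (95% CI) | Out of tested (95% CI) | FAS share if all untested had it |
|---|---|---|---|---|---|---|
| 50% | 150 | 10% | 15 | 5.0% (2.8–8.1) | 10.0% (5.7–16.0) | 55.0% |
| 81% | 243 | 10% | 24 | 8.0% (5.2–11.7) | 9.9% (6.4–14.3) | 27.0% |
| 81% | 243 | 25% | 61 | 20.3% (15.9–25.3) | 25.1% (19.8–31.0) | 39.3% |
| 90% | 270 | 10% | 27 | 9.0% (6.0–12.8) | 10.0% (6.7–14.2) | 19.0% |
| 100% | 300 | 10% | 30 | 10.0% (6.8–14.0) | 10.0% (6.8–14.0) | 10.0% |

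At r = 81% and p = 10%, for example, the SAP figure of 24/300 = 8.0% is the lower bound for the FAS. The upper bound is (24 + 57)/300 = 27.0%. The confidence interval around 8.0% does not express that range.

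**By visit.** SAP section 3.3.2 treats a participant with no value in a window as missing at that visit, and the four-weekly Week 28 window is days 183 to 210. Under Table 7 of the protocol, an uninterrupted taper from 40 mg starting at Week 4 reaches 5 mg at about Week 14 to 17, depending on whether the interval is counted before or after each step. The first test then falls at about Week 18 to 21, at the latest day 21 × 7 + 1 = 148, before the Week 28 window opens. A normal ACTH result needs no repeat (Protocol Table 3). If the windowing rule is applied literally, many first results lie outside the Week 28 window and the share tested within it could be well below the share ever tested. The SAP states no cumulative rule for this endpoint. How much lower cannot be computed from the documents.

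**The case against.** The strongest defence is that the FAS denominator is the declared default, that Protocol section 9.4.3.3 bases all exploratory analyses on the FAS, and that AI detected among all treated participants is a legitimate quantity. A tested-only figure is not neutral either. It conditions on a post-baseline outcome, having tapered to 5 mg, and leaves out those held at higher doses, whose AI status is unknown. This stands as a reason to keep the FAS figure alongside. It does not justify leaving that figure unlabelled, with no tested base and no count of the untested. The default itself allows exceptions, and the same section makes two.

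Untested participants are also not classed as normal; they fall in no row. That is correct, and it is why the normal row is diluted by the same factor.

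The final analysis will use AI status at 5 mg as a subgroup factor (SAP section 4.2.1.7), and those subgroup sizes would give counts on roughly the tested basis. This helps only partly: it is planned for Week 52 only, and it presents other endpoints by AI status instead of reporting AI.

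A reader might infer that the three sets of proportions cannot be read together. The documents do not support that. The sets are nested, since an indeterminate morning result leads to the ACTH test or the repeat cortisol, and counts are required beside the proportions. The number tested can be recovered by summing the three rows, provided each participant is counted once.

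**Conclusion.** The point holds as a presentation fault in an exploratory, descriptive endpoint. Followed as written, the SAP reports the proportion among the tested multiplied by the share tested. The relative understatement is the untested share: 50% at r = 50%, 19% at r = 81%, 10% at r = 90%, and none if everyone is tested. In absolute terms, 81% tested with 10% complete AI among the tested gives about 8% instead of about 10%. These sizes rest on assumed values of r and p. No primary or secondary endpoint depends on this table.

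A larger effect is tempting to infer. Protocol section 2.1 cites AI in about 50% of patients after OCS withdrawal. Multiplying that by an assumed 70% to 90% tested gives 35% to 45%, a shortfall of 5 to 15 points. The documents do not support that figure. The 50% is a background rate of AI after withdrawal in general, whereas the only AI row with an FAS denominator is complete AI on morning cortisol (below 100 nmol/L, or below 200 nmol/L with oestrogen-containing contraceptives; Protocol Table 9). Partial AI comes from the ACTH and repeat-cortisol sets, which already have conditional denominators. The assumed 70% to 90% has no source in the documents either.

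**What to change.** In SAP sections 4.2.14.2 and 4.2.14.4:

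1. Use participants with a morning cortisol result as the denominator for the normal, indeterminate and complete-AI proportions, reported as ever tested and cumulatively by Week 28 and by Week 52. State which result counts when a participant has more than one.
2. Add a *not tested* row out of the FAS, split into 5 mg not reached, withdrew, and missing.
3. If the FAS percentage is kept, show it alongside and label it as AI detected among all treated participants.

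The cost is SAP wording and one extra row, with no new data. The downside is that the tested-only figure describes only participants who tapered to 5 mg; the *not tested* row makes that selection visible.

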4.2.14.3 Handling of Dropouts and Missing Data

No data imputation.

4.2.14.4 Primary Analysis of Exploratory Endpoint

The number and proportions of participants with normal, indeterminate and complete AI based on morning cortisol test are summarised over time on the FAS. In addition, if the morning cortisol test is in indeterminate range, the number and proportions of participants with normal, partial and complete AI based on ACTH test as well as repeated morning cortisol test are presented.

4.2.14.5 Additional Analyses of Exploratory Endpoint

No additional analysis.

4.2.14.6 Subgroup Analyses of Exploratory Endpoint

No subgroup analysis.

4.2.14.7 Interim Analysis of Exploratory Endpoint

No presentation for interim analysis.

4.2.15 Exploratory Endpoint - Proportion of ACQ-6 responders at Week 28 and Week 52

4.2.15.1 Definition

The proportion of responders are summarised at each timepoint until and including Week 28 or Week 52. Individual changes of at least 0.5 are considered to be clinically meaningful and a decrease from baseline of at least 0.5 is the responder definition for ACQ-6.

4.2.15.2 Derivations

ACQ-6 responder (Yes=1/No=0) is calculated at each timepoint as follows:

- Responder: Absolute individual change from baseline in ACQ-6 score \leq -0.5
- Non-responder: Absolute individual change from baseline in ACQ-6 score > -0.5

The proportion of responders (non-responders) is calculated as the number of participants who reached the responder (non-responder) ACQ-6 threshold at each timepoint divided by total number of participants in the FAS.

Strategies of handling intercurrent events are presented in Section 4.2.

4.2.15.3 Handling of Dropouts and Missing Data

No data imputation.

4.2.15.4 Primary Analysis of Exploratory Endpoint

The number and proportions of ACQ-6 responders, non-responders and missing data are summarised over time on the FAS. Additionally, the percentage of ACQ-6 responders is displayed graphically over time.

4.2.15.5 Additional Analyses of Exploratory Endpoint

No additional analysis.

4.2.15.6 Subgroup Analyses of Exploratory Endpoint

No subgroup analysis.

4.2.15.7 Interim Analysis of Exploratory Endpoint

The derivation of ACQ-6 responder is presented in Section 4.2.15.2.

The number and proportions of ACQ-6 responders, non-responders and missing data are presented over time on the FAS.

4.2.16 Exploratory Endpoint - Proportion of AQLQ(s)+12 responders at Week 28 and Week 52

4.2.16.1 Definition

The AQLQ(s)+12 responders are summarised at Week 28 or Week 52. The responder definition for AQLQ(s)+12 is 0.5-point improvement from baseline.

4.2.16.2 Derivations

AQLQ(s)+12 responder (Yes=1/No=0) is calculated on the FAS at each timepoint as follows:

- Responder: Absolute individual change from baseline in AQLQ(s)+12 total score
 ≥ 0.5
- Non-responder: Absolute individual change from baseline in AQLQ(s)+12 total score < 0.5

The proportion of responders (non-responders) is calculated as the number of participants who reached the responder (non-responder) AQLQ(s)+12 threshold at each timepoint divided by total number of participants in the FAS.

Strategies of handling intercurrent events are presented in Section 4.2.

4.2.16.3 Handling of Dropouts and Missing Data

No data imputation.

4.2.16.4 Primary Analysis of Exploratory Endpoint

The number and proportions of AQLQ(s)+12 responders, non-responders and missing data are summarised over time on the FAS.

4.2.16.5 Additional Analyses of Exploratory Endpoint

No additional analysis.

